1. STATEMENT OF COMPLIANCE

The trial will be carried out in accordance with International Conference on Harmonization Good Clinical Practice (ICH GCP) and the following:

United States (US) Code of Federal Regulations (CFR) applicable to clinical studies (45 CFR Part 46, 21 CFR Part 50, 21 CFR Part 56, 21 CFR Part 312, and/or 21 CFR Part 812).

The protocol, informed consent form, recruitment materials, and all participant materials will be submitted to the Institutional Review Board (IRB) for review and approval. Approval of both the protocol and the consent form must be obtained before any participant is enrolled. Any amendment to the protocol will require review and approval by the IRB before the changes are implemented to the study. In addition, all changes to the consent form will be IRB-approved; a determination will be made regarding whether a new consent needs to be obtained from participants who provided consent using a previously approved consent form.

Document ID:	SRC_SLE_Sparkle EP 2_2021_11315	Document title:		Classification:	Confidential
Modified:	12 May 2021	Clinical Investigation Proto	Clinical Investigation Protocol ICH E6 Aligned		
Version:	1	User Tool ID:	16.2.6UserTool0004		
Status:	FINAL	User Tool Version Date	5June2019	Page:	9

2. PROTOCOL SUMMARY

2.1. Synopsis

	T			
Study Title & ID:	Validation of the DreamKit plethysmography-derived respiratory effort signal against esophageal pressure			
	SRC_SLE_Sparkle EP 2_2021_11315			
Project Name:	Sparkle			
Study Description:	This study has been developed in order to demonstrate the validity of the DreamKit respiratory effort signal against the gold-standard measurement of respiratory effort, esophageal pressure.			
Endpoint:	The primary endpoint is the intraclass correlation coefficient of the peak-to-peak breath amplitude sequences extracted from the DreamKit and esophageal manometry respiratory effort signals over a range of respiratory effort generated during periods of occluded inspiration, end-expiratory breath holds, increased inspiratory resistance, increased expiratory resistance, and unresisted shallow breathing.			
Hypothesis:	We hypothesize that the lower-bound of the 95% confidence interval for the correlation of breath amplitude sequences extracted from the DreamKit and esophageal manometry respiratory effort signals will be ≥0.5, indicating at least moderate agreement between the signals.			
Study Population:	Up to 20 participants will be enrolled in this study in order to complete data collection in n =10.			
	Inclusion Criteria:			
	Aged ≥18 years;			
	Fluent in English;			
	Able to provide informed consent.			
	Exclusion Criteria:			
	Contraindication to esophageal pressure monitoring, including a sensitive gag reflex (determined by a positive response to the screening question "do you sometimes or often gag while brushing"			

Document ID:	SRC_SLE_Sparkle EP 2_2021_11315	Document title:		Classification:	Confidential
Modified:	12 May 2021	Clinical Investigation Proto	Clinical Investigation Protocol ICH E6 Aligned		
Version:	1	User Tool ID:	16.2.6UserTool0004		
Status:	FINAL	User Tool Version Date	5June2019	Page:	10

-	
	your teeth?"), dysphagia, nasal obstruction, and/or esophageal disorder likely to impact placement of the balloon;
	Pregnancy or planned pregnancy during the study
	History of allergic reactions to medical adhesives;
	Known allergy to lidocaine;
	Known seizure disorder;
	 Severe medical condition (controlled or uncontrolled) impacting breathing including neuromuscular disease, chronic obstructive pulmonary disease, respiratory failure or insufficiency, or requirement for oxygen therapy;
	 Chronic cardiopulmonary or renal disease, including a history of irregular heart rhythms;
	At risk for excessive bleeding including use of anticoagulants;
	 An employee, or spouse of an employee, of a company that designs, sells, or manufactures sleep related products (including Philips);
	An employee, or spouse of an employee, of PCCAB.
Study Design:	This is an interventional study performed in a single center for algorithm validation.
Study Visit(s) Summary & Duration:	Visit 1 • Consent, medical history, anthropometrics, skin assessment. Visit 2
	 Respiratory effort data collection (esophageal manometry alongside the DreamKit device) under various breathing conditions.

Document ID:	SRC_SLE_Sparkle EP 2_2021_11315	Document title:		Classification:	Confidential
Modified:	12 May 2021	Clinical Investigation Proto	Clinical Investigation Protocol ICH E6 Aligned		
Version:	1	User Tool ID:	16.2.6UserTool0004		
Status:	FINAL	User Tool Version Date	5June2019	Page:	11

2.2. Schedule of Activities

Procedures	Performed by	Visit 1 (office)	Visit 2 (lab)
Informed Consent	PI or designee	Х	
Medical History & Anthropometrics	PI or designee	Х	
Skin pigmentation assessment	Study coordinator	Х	
Enrollment	Study coordinator	Х	
Data Collection & Monitoring	PI or designee		Х
AE Monitoring	Study coordinator	Х	Х
Participant Compensation & Study Dismissal	Study coordinator		Х
AE Monitoring phone call	Study coordinator		[1-2 days after Visit 2]

3. INTRODUCTION

3.1. Background

Home sleep apnea test (HSAT) devices are increasingly used to diagnose obstructive sleep apnea (OSA).¹ Potential advantages of taking the diagnostic process from the hospital to the home include reduced cost; increased access; reduced wait times; higher patient turnover; increased patient comfort; and the collection of data that is more representative of a patient's usual sleep. Drawbacks of the HSAT model include the reduced number of signals compared with polysomnography (PSG); reduced patient/provider contact thereby limiting the opportunity for OSA education/support; and increased possibility of configuration error or signal loss leading to the requirement for further testing.¹-³ Research has demonstrated that a lab-based diagnostic approach is not superior to a home-based approach in terms of self-reported daytime sleepiness, quality of life, blood pressure, and subsequent adherence to continuous positive airway pressure (CPAP) measured over four weeks.⁴ Development of a simpler HSAT device may be beneficial in terms of maximizing the collection of good quality signals, while also increasing ease of use and patient comfort. The DreamKit device has been designed to meet these needs.

The DreamKit device is a single-use adhesive patch containing an accelerometer and pulse oximeter, linked to nasal pressure cannula. From these three sensors, the following signals can be monitored or

Document ID:	SRC_SLE_Sparkle EP 2_2021_11315	Document title:		Classification:	Confidential
Modified:	12 May 2021	Clinical Investigation Proto	Clinical Investigation Protocol ICH E6 Aligned		
Version:	1	User Tool ID:	16.2.6UserTool0004		
Status:	FINAL	User Tool Version Date	5June2019	Page:	12

derived: nasal airflow, blood oxygen saturation (SpO₂), pulse rate, respiratory effort, sleep time, and head position. The adhesive patch containing the pulse oximeter is designed to be placed on the forehead, connected to adhesive nasal pressure cannula placed over the nasal bridge and directly below the nostrils. Data are stored in the flash memory on the device, and can be uploaded to a computer upon completion of the recording.

4. OBJECTIVES

4.1. Primary Objective, Endpoint, and Hypothesis

The objective of this study is to validate the DreamKit plethysmography-derived respiratory effort signal against the gold standard, esophageal pressure, in ten healthy participants during a single in-laboratory daytime visit.

The primary endpoint is the intraclass correlation coefficient (ICC) of the peak-to-peak breath amplitude sequences extracted from the DreamKit and esophageal manometry respiratory effort signals during periods of occluded inspiration, end-expiratory breath holds, increased inspiratory resistance, increased expiratory resistance, and unresisted shallow breathing. We hypothesize that the lower-bound of the 95% confidence interval for the correlation of breath amplitude sequences extracted from the DreamKit and esophageal manometry respiratory effort signals will be ≥0.5, representing at least moderate agreement between the signals.⁵

4.2. Exploratory Objectives

Our exploratory objectives are:

- To repeat the analysis for the primary objective for each participant individually.
- Within the periods of occluded inspiration (representing obstructive apneas) and end-expiratory breath-holds (representing central apneas), to categorize each respiratory effort signal as being above or below a threshold of 10% of the baseline amplitude derived from normal (relaxed) breathing, in order to calculate sensitivity, specificity, and the area under the receiver operating characteristic (ROC) curve for the detection of obstructive events (overall and for each participant individually).
- Within the periods of increased inspiratory and expiratory resistance (representing obstructive hypopneas) and unresisted shallow breathing (representing central hypopneas), to calculate the area under the ROC curve in order to assess the agreement between the respiratory effort signals across all possible thresholds.

Document ID:	SRC_SLE_Sparkle EP 2_2021_11315	Document title:		Classification:	Confidential
Modified:	12 May 2021	Clinical Investigation Protocol ICH E6 Aligned			
Version:	1	User Tool ID:	16.2.6UserTool0004		
Status:	FINAL	User Tool Version Date	5June2019	Page:	13

- To compare the number of breaths/minute between esophageal manometry and the DreamKit device during relaxed breathing, fast breathing, slow breathing, occluded inspiration, increased inspiratory resistance, increased expiratory resistance, and unresisted shallow breathing.
- To evaluate the phase relationship between esophageal manometry and the DreamKit device during relaxed breathing, fast breathing, slow breathing, occluded inspiration, increased inspiratory resistance, increased expiratory resistance, and unresisted shallow breathing.

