5.2.3. Adoption of respiratory effort amplitude as the primary endpoint

The three characteristics of a continuous signal are amplitude (in this case, respiratory effort in pressure units of cmH₂O), frequency (in this case, breathing rate), and phase (in this case, time alignment of the two signals). The most clinically-relevant of these characteristics is amplitude, as the only component of the respiratory effort signal taken into account when scoring PSGs and HSATs is whether or not respiratory effort is present or absent during apneic events or whether there is reduction in respiratory effort that is proportional to the flow reduction during hypopneic events (AASM scoring criteria; Version 2.6). We will undertake exploratory analyses of respiratory rate (breaths/minute) and phase (time alignment).

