Data from the DreamKit device will not be visible in real-time, and therefore it is important to ensure that the DreamKit signals can be synchronized to the esophageal pressure signals post-hoc. At the beginning and end of the data collection period, the participant will be asked to breathe out and hold their breath for approximately three seconds; then take a deep breath in and hold for approximately three seconds; and then finally, tap the DreamKit device to coincide with the peak of inhalation. This process will place a motion artefact on the accelerometry signal timed (approximately) to inhalation observed in the respiratory effort and esophageal pressure signals. The SpO₂ signals collected via the Alice 6 and the DreamKit device may also be used for time-alignment. During data processing, it may be necessary to make a small adjustment to the DreamKit time to match the Alice 6 time, ensuring synchronization of the signals.

Data Collection

Participants will be instructed to undertake the following breathing conditions (all in the supine position):

- End-expiratory breath holds to mimic central apneas: ten breath holds after exhalation, 10-20 seconds in duration.
- Occluded inspiration to mimic obstructive apneas: five periods of occluded inspiration paced at 15 attempted breaths/minute with blocked nose and mouth closed, 10-20 seconds in duration.
- Increased inspiratory resistance to mimic obstructive hypopneas and RERAs: paced at 15 breaths/minute against inspiratory resistance using the Philips IMT device (see details below), for 30 seconds at a time, five times.
- Increased expiratory resistance to mimic obstructive hypopneas and RERAs: paced at 15 breaths/minute against expiratory resistance using the Philips Threshold PEP device (see details below), for 30 seconds at a time, five times.
- Shallow breathing to mimic central hypopneas: partial breaths paced at 15 breaths/minute without resistance, for 30 seconds in duration, five times.
- Slow: paced at 12 breaths/minute; two minutes.
- Fast: paced at 20 breaths/minute; two minutes.
- Relaxed: paced at 15 breaths/minute; two minutes.

The coordinator will allow the participant time to become comfortable and still before beginning each condition, and will note the exact start/end time of each (MM:SS) from the computer used for data collection.

The participant may return to relaxed breathing at any time if they experience discomfort or dizziness.

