For the paced breathing conditions, the site coordinator will play a metronome (e.g. www.imusic-school.com/en/tools-online-metronome) set to 24 (slow), 30 (relaxed) and 40 tones per minute (fast), allowing the participant to time each inspiration and expiration to the tones for breathing rates of 12, 15, and 20 breaths per minute.

Document ID:	SRC_SLE_Sparkle EP 2_2021_11315	Document title:		Classification:	Confidential
Modified:	12 May 2021	Clinical Investigation Protocol ICH E6 Aligned			
Version:	1	User Tool ID:	16.2.6UserTool0004		
Status:	FINAL	User Tool Version Date	5June2019	Page:	21

Increased inspiratory resistance will be achieved with the Philips Threshold IMT breathing trainer, a small, hand-held mouthpiece containing a flow-independent one-way valve¹. Similarly, increased expiratory resistance will be achieved with the Philips Threshold PEP device, a device which creates positive pressure during exhalation². The pressure of each device can be adjusted in 2cmH₂O increments. During data collection, the coordinator should coach the participant and adjust the pressure of each device when necessary in order to achieve appropriate changes in pressure during increased inspiratory and expiratory resistance conditions. Participants should aim to achieve a change from normal breathing of at least -15mmHg, but ideally -20 to -30mmHg, during the increased inspiratory and expiratory resistance conditions, and ensure a minimal change in esophageal pressure during the end-expiratory breath holds compared to normal breathing. A previous study following similar methodology to simulate apneas found a median change in esophageal pressure compared to normal breathing of -20.1mmHg (quartiles -21.9 to -15.0) with increased inspiratory resistance, -29.1mmHg (quartiles -38.4 to -20.6) with increased expiratory resistance, and 0.1mmHg (quartiles -2.9 to 2.0) with end-expiratory central apnea.^{10,11}

The data collection period is likely to be approximately one hour per participant, and will not exceed 1.5 hours. At this time, all equipment will be removed and the participant will be free to leave the laboratory.

Data processing

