12.2.5. Exploratory Analyses

The methodology described above for the primary analysis will be repeated using data from each participant individually.

Within the occluded inspiration and end-expiratory breath holds (representing obstructive and central apneas, respectively), we will categorize each signal as being above or below a threshold. Each period will be identified as a true positive for obstructive apnea (esophageal manometry scored as occluded inspiration and DreamKit signal above the threshold), true negative (esophageal manometry scored as breath-hold and DreamKit signal below the threshold), false positive (esophageal manometry signal scored as breath hold but DreamKit signal above the threshold), or false negative (esophageal manometry signal scored as occluded inspiration but DreamKit signal below the threshold). This will allow us to calculate the sensitivity, specificity, and area under the ROC curve for the ability of the DreamKit signal to identify obstructive apnea events. The threshold for calculating sensitivity and specificity will be 10% of the baseline amplitude derived from normal (relaxed) breathing. This threshold corresponds to a proportional change in respiratory effort for an apneic event that requires a 90% reduction of flow amplitudes as compared to the baseline respiration.

Document ID:	SRC_SLE_Sparkle EP 2_2021_11315	Document title:		Classification:	Confidential
Modified:	12 May 2021	Clinical Investigation Protocol ICH E6 Aligned			
Version:	1	User Tool ID:	16.2.6UserTool0004		
Status:	FINAL	User Tool Version Date	5June2019	Page:	28

Within the increased inspiratory/expiratory resistance and shallow breathing periods (representing obstructive and central hypopneas), we will calculate the area under the ROC curve which will provide an aggregate assessment of agreement between the two respiratory effort signals across all possible thresholds. Unlike apneas, the classification of hypopneas as obstructive or central is not based on the presence or absence of respiratory effort (AASM scoring criteria; Version 2.6), and therefore we will not categorize each breathing period on the basis of a respiratory effort threshold.

The respiratory rate will be extracted from each breathing condition except breath holds, and we will provide a Bland-Altman analysis of respiratory rate between the esophageal pressure signal and the DreamKit device.

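### The exploratory hypopnea ROC separates shallow from strongly resisted breathing without a normal-effort comparator, so a high area would not show that DreamKit detects reduced effort

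*Combined protocol and SAP*

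**What the plan says.** Section 4.2 (third bullet) restricts the analysis to data "Within the periods of increased inspiratory and expiratory resistance (representing obstructive hypopneas) and unresisted shallow breathing (representing central hypopneas", and Section 12.2.5 repeats the restriction: "Within the increased inspiratory/expiratory resistance and shallow breathing periods (representing obstructive and central hypopneas". Of the result, 12.2.5 says: "we will calculate the area under the ROC curve which will provide an aggregate assessment of agreement between the two respiratory effort signals". It names no reference label, unit of analysis or target value, and it declines to classify hypopnea periods by an effort threshold.

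Section 9.1.3 sets the size of the resisted efforts: "Participants should aim to achieve a change from normal breathing of at least -15mmHg, but ideally -20 to -30mmHg". It gives no pressure target for shallow breathing. It does record a normal-effort block at the same pace as the shallow and resisted periods: "Relaxed: paced at 15 breaths/minute; two minutes". That block supplies the 10% threshold for the apnea analysis and enters the rate and phase analyses, but not the hypopnea ROC.

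Section 5.2.3 gives the feature of effort that scorers use in hypopneas: "whether there is reduction in respiratory effort that is proportional to the flow reduction during hypopneic events".

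**The concern.** An ROC area depends only on how two sets of amplitudes are ranked against each other. One set here is pushed well above normal by coaching. The other is meant to lie below normal. A device signal can rank them correctly because it rises in the resisted periods, because it falls in the shallow periods, or both, and the area does not say which. The feature in Section 5.2.3 is the fall. A device whose signal stayed at its normal level during shallow breathing could still get a high area.

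The intended-use text in Section 4.3 covers classifying hypopneas as central, mixed or obstructive. A high area could be cited for the central-hypopnea part of that statement without having tested it.

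**Working it through.** The documents state no expected area, so there is no figure to reproduce. The question is what area a device would get if it tracks resisted effort fully but shows no fall during shallow breathing.

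**Ratio model.** Assumptions, none of them in the documents:
- Normal swing 5 to 10 mmHg. With the 15 mmHg aim, the resisted/relaxed amplitude ratio R is (5 + 15)/5 = 4 down to (10 + 15)/10 = 2.5.
- True shallow/relaxed ratio 0.5.
- Lognormal amplitudes with the same log-scale noise SD, s, in both classes, from 0.3 to 0.7.

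Then area = Φ(ln(ratio) / (s√2)). For resisted versus shallow the ratio is R/1 for the no-fall device and R/0.5 for the device that halves its amplitude. For shallow versus relaxed it is 2 for the halving device and 1 for the no-fall device.

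| Contrast | Device | s = 0.3 | s = 0.5 | s = 0.7 |
|---|---|---|---|---|
| Resisted v shallow, R = 2.5 | no fall | 0.985 | 0.902 | 0.823 |
| Resisted v shallow, R = 2.5 | halves | 1.000 | 0.989 | 0.948 |
| Resisted v shallow, R = 4 | no fall | 0.999 | 0.975 | 0.919 |
| Resisted v shallow, R = 4 | halves | 1.000 | 0.998 | 0.982 |
| Shallow v relaxed | no fall | 0.500 | 0.500 | 0.500 |
| Shallow v relaxed | halves | 0.949 | 0.837 | 0.758 |

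The two devices differ by 0.00 to 0.13 on the planned contrast (largest 0.948 − 0.823) and by 0.26 to 0.45 on shallow versus relaxed. On the log scale, the resisted increase supplies ln 2.5 / ln 5 = 0.916/1.609 = 57% of the halving device's separation at R = 2.5, and ln 4 / ln 8 = 1.386/2.079 = 67% at R = 4.

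**Additive model, using the figures in Section 9.1.3.** From a previous study it reports these pressure changes (the first figure is also negative): "20.1mmHg (quartiles -21.9 to -15.0) with increased inspiratory resistance, -29.1mmHg (quartiles -38.4 to -20.6) with increased expiratory resistance". Spread around zero change is taken from the breath-hold figure in the same sentence, "0.1mmHg (quartiles -2.9 to 2.0) with end-expiratory central apnea". With SD = interquartile width / 1.349:
- inspiratory resistance: 6.9/1.349 = 5.1 mmHg
- expiratory resistance: 17.8/1.349 = 13.2 mmHg
- breath hold, as a proxy for a signal with no change: 4.9/1.349 = 3.6 mmHg

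Area for the no-fall device = Φ(Δ / √(SD₁² + SD₂²)):
- inspiratory: Φ(20.1/√(5.1² + 3.6²)) = 0.999
- expiratory: Φ(29.1/√(13.2² + 3.6²)) = 0.983
- with a further 10 mmHg of noise SD in each class: 0.903 and 0.930

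**Pooled simulation.** Ten participants, ten resisted and five shallow periods each, the 9.1.3 medians and spreads, assumed normal amplitude 5 to 10 mmHg, noise SD 2 to 10 mmHg and between-participant log-gain SD 0 to 0.8. The no-fall device got 0.82 to 0.995 and the halving device 0.88 to 0.999. A device whose signal rose by 50% during shallow breathing got 0.74 to 0.99.

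**Less favourable settings.** The 15 mmHg is an aim. In the cited study the inspiratory quartile nearest zero was −15.0, so about a quarter of changes were smaller. A 10 mmHg change on an assumed 10 mmHg swing gives R = 2, and at s = 0.7 the no-fall device gets Φ(0.693/0.990) = 0.758. In the additive model, 15 mmHg with a per-class SD of 20 mmHg gives Φ(15/28.3) = 0.702.

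**The case against.** The strongest reply is that obstructive versus central is the right contrast for the Section 4.3 statement. It parallels the apnea ROC (occluded inspiration versus breath hold), and relaxed breathing mimics neither event. That stands. The planned area is a legitimate description, and shallow versus relaxed is a further question, not a replacement.

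The hypopnea conditions also enter other analyses: the primary ICC, its per-participant repeat, and the rate and phase analyses. A reader might infer that the ROC is the only hypopnea analysis, and it is not. But both ICC analyses mix shallow breathing with four other conditions and leave out relaxed breathing, and rate and phase do not measure amplitude. None of them isolates a fall in effort.

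A reader might also take Section 5.2.3 to require comparison with a relaxed baseline. It speaks of a reduction proportional to the flow reduction and names no baseline. Relaxed breathing is proposed here because it is the normal-effort block on record and already anchors the apnea threshold.

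Resisted versus shallow is itself inferred, since no reference label is given. If the label were derived from esophageal amplitude, the figures above would not apply directly, although normal effort would still be missing from the data used.

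Finally, no target or claim is tied to this area, so any misuse of it is a possibility and not something the plan states.

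**Conclusion.** The point holds as a limit on interpretation. On the natural reading, a high hypopnea area shows mainly that DreamKit registers large coached increases in effort. It does not show that the device detects a reduction.

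The range of 0.82 to 1.00 for a device with no fall, against 0.95 to 1.00 for one that halves its amplitude, is conditional. It rests on the assumed ratio and noise, on full tracking of resisted effort, and on treating the coached pressure change as a change in peak-to-peak amplitude. Smaller achieved changes or more noise bring the no-fall device to about 0.70 to 0.76, still well above 0.5.

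Two stronger readings are not supported. The documents do not suggest that DreamKit fails to register shallow breathing; the no-fall device is only a test case. Nor do they make the planned contrast an error. The analysis is exploratory, has no success criterion and leaves the primary hypothesis untouched. The change is still worth making, because it is cheap and would let the analysis show a fall in effort.

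**What to change.** In Section 4.2 (third bullet) and Section 12.2.5:
- Keep the resisted-versus-shallow area, state its reference label and unit of analysis, and describe it as the obstructive/central contrast.
- Add two within-participant areas, shallow versus relaxed and resisted versus relaxed, each for DreamKit and for esophageal amplitude side by side. The esophageal area also shows whether shallow breathing really lowered effort, since Section 9.1.3 sets no target for it.
- Base any statement about detecting reduced effort in central hypopneas on the shallow-versus-relaxed area.

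The data are already collected: two minutes of relaxed breathing give 120/30 = four 30-second segments, or 2 × 15 = about 30 breaths, per participant. The cost is SAP wording and a little programming. The downsides are that the shallow-versus-relaxed area will look less favourable, and that the relaxed segments come from one block per participant and are correlated, so they should not be treated as independent.
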